#### Additional Baseline Instruments

9	Patient Health Questionnaire-9 PHQ-9	Reliability: Cronbach's Alpha 0.96 Validity: $r = 0.62- 0.90$ $p < .001$	PHQ-9 is a nine-item depression self-report module from the full Patient Health Questionnaire. Scores range from 0-27. (9 items, 2-5 min)	Objective 5. To determine the presence of an often co-occurring health issue, depression, with mTBI prolonged symptoms. Estimates as high as 34% of mTBI SMs with depression.
10	Posttraumatic Stress Disorder Checklist PCL-5	Reliability: Cronbach's Alpha 0.89 Validity: Sensitivity 84% Specificity 72%	The PCL-5 is a 20-item questionnaire, corresponding to the DSM-5 symptom criteria for PTSD. The wording of PCL-5 items reflects both changes to existing symptoms and the	Objective 5. To determine the presence of an often co-occurring health issue, PTSD, with mTBI. Estimates as

		r = 0.89	addition of new symptoms in DSM-5. (20 items, 5-10 min)	high as 60% of SMs with mTBI with PTSD.
--	--	----------	---	---

Table 5 depicts the schedule of administration for each of the tools used in this study.

Table 5. Assessment Tool Schedule of Administration by Group							
Assessment Tool		Schedule of Administration					Group
No	Abbreviated Name	Initial: at -1 week	Mid: at 4-6 weeks [±1 week]	End: at 8-10 weeks [±2 weeks]	2-Month Follow-up	Other	Intervention and Control
1	HIT-6	x	x	x	x		x
2	ISI	x	x	x	x		x
3	QIKtest	x	x	x	x		x
4	NEUROQOL TBI	x	x	x	x		x
5	QOL ABRI	x	x	x	x		x
6	GSI	x	x	x	x	At each session*	x
7	Demographic Data Form**	x	x	x	x		x
Additional Baseline Instruments							
8	PHQ-9	x	x	x	x		x
9	PCL-5	x	x	x	x		x
10	DASS-21	x	x	x	x		x
		* An abbreviated symptom inventory based on participant's primary symptoms will be administered at each NFB session to assist with treatment planning. **Current medications, diagnoses, and treatments that were indicated initially on Demographic data will be checked at the 3 assessment sessions to see if any deletions or additions occurred during course of study intervention.					

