## Statistical and Data Analysis Plan

The analyses will be conducted based on intention-to-treat principle (Friedman, Furberg, DeMets, 2010) where participants are analyzed according to their group assignment regardless of the treatment received (e.g., switching treatments or poorly adhering to assigned treatment). Patient demographics will be presented using frequencies and percentages for categorical variables and means and standard deviations for continuous variables. Although balance between intervention arms will be guaranteed by randomization, there may be unmeasured confounding. Two sample t tests or chi-square tests will be conducted to investigate potential confounding effects on demographic variables.

For each hypothesis, first two sample t-tests will be utilized to assess the effect of NFB intervention at each time. Then, a repeated-measures analysis of variance (ANOVA) will be implemented for the outcome variable that shows significant group effect. The mixed effects model will include group (between-factor), time (within-factor), and the interaction between group and time as fixed effects. From this model, the interaction will allow the testing of whether longitudinal trajectory is associated with group assignment. The longitudinal trajectory from baseline, 4-6-week and 8-10-week to 2-month follow-up, for each outcome of interest will be investigated in this model accounting for covariance structure (e.g., AR(1)) within participants. This determines the rate of improvement during the course of the intervention. Any baseline subject characteristics found to differ between groups as covariates to assess the impact of the baseline covariates on the effectiveness of the intervention over the course of the study will also be included if needed].

The outcomes of interest for each hypothesis are clinically significant:

- 1) Reduction in frequency, severity and/or impact of headaches: HIT-6 and NEUROQOLTBI
- 2) Improvement of perceptions of quality of sleep and insomnia severity: ISI and NEUROQOLTBI Sleep disturbance
- 3) Improvement in attention function: QIK-Test
- 4) Improvement in the quality of life: QOLIABRI and NEUROQOLTBI Satisfaction & Participation in roles and activities

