## 5) Improvement in the general physical and emotional symptoms: GSI, DASS21, PHQ9, PSL-5 and NEUROQOLTB Positive affect and wellbeing.

As a secondary analysis, a per-protocol analysis will investigate the effect of the intervention in participants that adequately adhere to the intervention, e.g., participants that attend over half of the treatment sessions versus participants attend less half of the treatment sessions. For all analyses, model assumptions will be evaluated with graphical and formal statistical tests such as Kolmogorov-Smirnov goodness-of-fit test. If there is marked nonlinearity or non-normality, transformation of the dependent variable or using a different link function such as the log link function will be considered. All analyses will be done in SAS version 9.4 on a non-VA Computer with two-tailed tests and P-value < 0.05 will be considered statistically significant.

Other statistical analyses not run by the biostatistician will be completed by the research team within the VA Informatics and Computing Infrastructure (VINCI) workspace.

**Power:** Power: Literature on NBF studies of patients with TBI have reported dropout rates ranging from 10% to 30% (Nelson & Esty, 2012; Zoeful, Huster, & Herrmann, 2011). Assuming a dropout rate of 28% and a moderate autocorrelation of 0.6 among repeated measures, this sample size will ensure to detect at least significant difference of 0.49 standard deviation with a power of 80% in the NFB intervention group compared to the control group with two-tailed significance level of 0.05 based on Diggle's et al (2002) approach for 4 repeated measures. This indicates that differences of less than 15% can be detected for HIT-6 (5.8% based on Cerritelli, 2015) and QOLABRI (13.8% based von Steinbuechel et al, 2016) and less than 26% for ISI (17.9% based on Nguyen, 2017) and DASS21 (19.7% based on Arundine et al., 2012) questionnaires. Thus, differences of 15% to 25% in the study instruments would be clinically significant. In addition, this study will detect a difference of at least 0.67 standard deviation if multiple testing is adjusted using FDR, which also provides a moderate effect size.

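### No outcome's own baseline score is pre-specified as a covariate: the gating t-tests ignore it, the conditional second-stage model uses it only as a first response, and other covariates depend on observed imbalance

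*Combined protocol and SAP*

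**What the plan says.** All passages here are in the combined protocol and SAP, mostly under Statistical and Data Analysis Plan.

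- Stage one: "first two sample t-tests will be utilized to assess the effect of NFB intervention at each time". No baseline term is mentioned.
- Stage two: a repeated-measures model "will be implemented for the outcome variable that shows significant group effect". Its fixed effects are group, time and their interaction, and baseline is one of the four modelled time points. The formal test is that "the interaction will allow the testing of whether longitudinal trajectory is associated with group assignment", "accounting for covariance structure (e.g., AR(1)) within participants".
- Covariates: "Any baseline subject characteristics found to differ between groups as covariates" "will also be included if needed". The only imbalance tests described are on demographic variables. There is no threshold and no covariate list.
- Data available: "Table 5 depicts the schedule of administration for each of the tools used in this study", and it marks every outcome instrument at the initial visit and at all three later ones.
- The Power paragraph assumes "a moderate autocorrelation of 0.6 among repeated measures" and does not say whether this is constant across visits or a lag-1 value.

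**The concern.** A participant's starting score is usually the best single predictor of the later score on the same instrument. Here it is collected for every outcome and then left out of the test that decides whether an outcome is modelled at all. Where the model is reached, baseline acts as a response, so the group-by-time contrasts are differences in change from baseline. That is a form of baseline handling, but less efficient than covariate adjustment whenever the correlation is below 1.

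With about 36 completers per arm there is little precision to spare, and the gate compounds the loss because an outcome missed by the weaker test never reaches the model. Separately, a covariate rule triggered by observed differences, and then left to judgement, lets the final model be settled after the data are seen.

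**Working it through.** **Inputs.** 36 completers per arm (Accessible Population and Methods of Recruitment); 0.49 SD, two-tailed 0.05 and correlation 0.6 (Power paragraph). Two assumptions are added: the effect is 0.49 SD at each post-baseline visit, and SDs are equal over time.

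**The plan's own figure.** The time-averaged formula for four measures with constant correlation 0.6 has variance factor (1 + 3×0.6)/4 = 0.70. At 36 per arm and 80% power the detectable difference is (1.96 + 0.842)×√(2×0.70/36) = 0.553 SD two-sided. A one-sided 0.05 gives (1.645 + 0.842)×0.197 = 0.490 SD. So the stated 0.49 is not reproduced at the stated two-tailed level under this reading. That is a separate matter; 0.49 serves below only as an illustrative effect.

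**Formula.** Power = Φ(0.49/√(2v/36) − 1.96), where r is the correlation between baseline and the visit, and v is
- visit t-test: 1
- change from baseline: 2(1 − r)
- adjusted for baseline: 1 − r²

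Against the t-test, adjustment lowers variance by r². Against change, the ratio is (1 − r²)/(2(1 − r)) = (1 + r)/2, a reduction of (1 − r)/2.

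**Constant 0.6.** t-test: 0.49/0.2357 = 2.079, power 54.7%. Change: v = 0.80, 0.49/0.2108 = 2.324, power 64.2%. Adjusted: v = 0.64, 0.49/0.1886 = 2.599, power 73.8%.

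**AR(1), lag-1 value 0.6, equal spacing.**

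| Visit | r | t-test | Change: v, power | Adjusted: v, power |
|---|---|---|---|---|
| Mid | 0.600 | 54.7% | 0.80, 64.2% | 0.640, 73.8% |
| End | 0.360 | 54.7% | 1.28, 45.1% | 0.870, 60.6% |
| Follow-up | 0.216 | 54.7% | 1.568, 38.2% | 0.953, 56.7% |

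Taking the visits at about 5, 9 and 17 weeks, with 0.6 applying over 5 weeks, r is 0.600, 0.399 and 0.176, and adjusted power is 73.8%, 62.1% and 56.0%.

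**The gate.** Simulating the three correlated post-baseline t-tests, at least one is significant in 76.4% of trials (constant 0.6) or 78.5% (AR(1)). An outcome with this effect would therefore fail to reach the model through those visits in roughly 24% or 22% of trials.

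**Joint tests.** With noncentrality (36/2)·δ′V⁻¹δ and δ = (0.49, 0.49, 0.49), the planned 3-df group-by-time test has 66% power (constant) or 50% (AR(1)). A 3-df test of group across the three baseline-adjusted visits has 83% or 71%. These are different tests, but both are null if treatment does nothing and baseline is unaffected by allocation.

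**One slope or three.** The adjusted figures need a separate baseline slope at each visit. A single common slope with unstructured covariance settles near 0.45 under AR(1). Follow-up variance is then 1 − 2×0.45×0.216 + 0.45² = 1.01, slightly worse than unadjusted. With the 5/9/17-week spacing the slope is about 0.44 and the variance 1.04.

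**If baseline is affected by allocation.** Suppose one arm's baseline shifts by 0.30 SD (assumed) and the shift does not persist. The visit-specific adjusted estimate is biased by 0.30r: 0.18, 0.11 and 0.06 SD under AR(1). The planned change contrast moves by the full 0.30 SD, and the unadjusted comparison does not move.

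**The case against.** A reader might infer that the plan makes no use of baseline at all. The documents do not support that: the second-stage model includes baseline, and its interaction compares change between arms. What stands is narrower. Baseline is never a covariate, and it is used only for outcomes that clear an unadjusted gate.

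A reader might also infer that the unadjusted tests are invalid. They are not. In simulated null trials at constant 0.6, the end-of-treatment t-test and the adjusted test both reject near 5%. Only within the 29% of trials with baseline imbalance above 0.25 SD do they part (11.8% against 5.1%), which is a conditional property and not bias in the design.

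Further fair points:

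- The magnitudes are illustrative. The only SDs over time in the documents, from a four-person pilot, are far from equal for some scales (QIK 17.53 to 0.96, GSI 7.94 to 22.91), and 0.49 SD was quoted for a four-measure calculation, not for one visit.
- The covariate sentence is garbled and may intend effect modification. On either reading it names no outcome baseline and depends on observed differences.
- AR(1) is offered as an example, so the plan is not committed to it.
- Adjustment can do harm if baseline was reported after allocation was known. The text at the end of Consenting Procedures, Table 6, Enrollment, and the placing of the baseline session under procedures for enrolled participants all put randomisation first. Pre-Enrollment and Enrolled Procedures lists the baseline session as pre-enrolment. This objection stands and governs which analysis should lead.

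**Conclusion.** The point holds as a loss of precision and a loosely specified model, not as a flaw in unconditional validity. At baseline correlation 0.6, one-visit power is about 55% unadjusted, 64% on change and 74% adjusted. Under AR(1), adjustment gains 19, 6 and 2 percentage points over the t-test (mid, end, follow-up) and 10, 15 and 18 or 19 points over the change contrast. Low correlation therefore does not rescue the plan: where the t-test loses least, the planned change contrast loses most.

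These sizes rest on 36 per arm, 0.49 SD at every post-baseline visit, equal SDs over time and the two readings of 0.6 shown; they are not bounds. A claim that any baseline-adjusted model beats the planned tests would go too far, because a common slope can do worse than no adjustment at follow-up. The advantage also presumes that baseline was unaffected by allocation, which the documents leave unsettled.

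**What to change.** 1. For every outcome, pre-specify a mixed model of the three post-baseline visits with group, visit, group-by-visit, that outcome's baseline score and baseline-by-visit, with unstructured covariance.
2. Name one deciding contrast, for example the adjusted group difference at end of treatment. The group-by-visit interaction should not decide: with baseline no longer a response, it has no power against an effect that is constant across the three visits.
3. Delete the t-test gate and the imbalance-driven covariate rule for this analysis, and report baseline characteristics descriptively.
4. Reconcile the order of randomisation and baseline. If baseline comes first, make the adjusted analysis primary. If it followed known allocation, state in advance that the unadjusted post-baseline comparison takes priority, with the adjusted one as supporting.
5. State a rule for participants with no baseline score, who otherwise drop out of the adjusted model.
6. Date the amendment and record whether outcomes by arm had been seen. Data Protection says participant procedures were complete as of March 2025; if outcomes had been seen, label the analysis post hoc.

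The cost is a short SAP amendment, no new data, and up to three degrees of freedom per model. The substantive risk is the bias shown above if baseline was affected by allocation, which is why item 4 must be settled first.

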## 5) Improvement in the general physical and emotional symptoms: GSI, DASS21, PHQ9, PSL-5 and NEUROQOLTB Positive affect and wellbeing.

As a secondary analysis, a per-protocol analysis will investigate the effect of the intervention in participants that adequately adhere to the intervention, e.g., participants that attend over half of the treatment sessions versus participants attend less half of the treatment sessions. For all analyses, model assumptions will be evaluated with graphical and formal statistical tests such as Kolmogorov-Smirnov goodness-of-fit test. If there is marked nonlinearity or non-normality, transformation of the dependent variable or using a different link function such as the log link function will be considered. All analyses will be done in SAS version 9.4 on a non-VA Computer with two-tailed tests and P-value < 0.05 will be considered statistically significant.

Other statistical analyses not run by the biostatistician will be completed by the research team within the VA Informatics and Computing Infrastructure (VINCI) workspace.

**Power:** Power: Literature on NBF studies of patients with TBI have reported dropout rates ranging from 10% to 30% (Nelson & Esty, 2012; Zoeful, Huster, & Herrmann, 2011). Assuming a dropout rate of 28% and a moderate autocorrelation of 0.6 among repeated measures, this sample size will ensure to detect at least significant difference of 0.49 standard deviation with a power of 80% in the NFB intervention group compared to the control group with two-tailed significance level of 0.05 based on Diggle's et al (2002) approach for 4 repeated measures. This indicates that differences of less than 15% can be detected for HIT-6 (5.8% based on Cerritelli, 2015) and QOLABRI (13.8% based von Steinbuechel et al, 2016) and less than 26% for ISI (17.9% based on Nguyen, 2017) and DASS21 (19.7% based on Arundine et al., 2012) questionnaires. Thus, differences of 15% to 25% in the study instruments would be clinically significant. In addition, this study will detect a difference of at least 0.67 standard deviation if multiple testing is adjusted using FDR, which also provides a moderate effect size.

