In addition, the Principal Investigator (PI) of this current project had previously collected comprehensive outcome data in private practice. Among 432 clients seen over a five-year period, only a small percent of clients, less than 5% (n=19) did not complete their course of treatment of 10-40 sessions. The number of sessions depended on an agreed amount from the outset of care. Three clients moved (1 continued NFB with another provider), 1 mother with 3 children returned to work and felt she could not continue, but hoped to return, and 15 did not give the PI of this project a reason for leaving, although 2 had indicated finances were an issue.

All clients were asked to identify their top 5 symptoms that they wanted to address, and invariably sleep issues was one of their choices. At the start of each session, the client was asked to rate their experience on the 5 symptoms on a 1-5 scale. Without exception, it was found that sleep was the first symptom positively impacted.

Post treatment, there was a large percent (94%) of clients meeting or exceeding their outcome goals, which were established prior to treatment, and 6% who did not entirely meet their goals but indicated satisfaction with

what was achieved. Clients came in for NFB for a variety of reasons, stress/anxiety [n= 103], attention issues (both adult and children) [n= 88], pain syndromes [n= 32], headache (migraine, tension, and mixed type) [n= 60], depression [n= 23], sleep [n= 25], and other [n=99] (i.e., irritable bowel syndrome, attachment disorder, etc. as well as those who wanted peak performance training). With the success with NFB in the civilian population, the PI of this project wants to bring NFB to VAPIHCS Veterans to provide an effective non-pharmacological solution to address very significant and often debilitating health issues.

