Twenty, one-hour, NFB training sessions will be provided to each participant in the intervention group by a trained NFB specialist over an 8-10-week period. Participants in the intervention group will receive up to 5-sessions but usually 3 sessions a week. Participants in the control group will continue with their usual treatment and will receive a 15-minute call for eight weeks from an Investigator on a health topic. This will help to keep members of the control group engaged in the project and receive the same information that is offered to the intervention group members. The health topics that are generally discussed during NFB sessions include sleep hygiene, basic nutritional concepts, beverage choices, positive thinking, thought reframing, fitness, daily calming activity, and enhancement of focus strategies. When a control group member completes his or her final assessment, he or she will be offered the NFB intervention over an 8-10-week period and will become part of the post-control intervention group.

Similar to other types of physiological training, it takes repeated exposure for the physiological learning, in this case demonstrated by the brainwaves to consolidate. According to published literature, 15 to 30 sessions (mean of 20 sessions), have been used in NFB training related to headaches; (Moshkani Farahani et al, 2014; Naderi & Jorjorzadeh, 2015; Nelson & Esty, 2015) usually 2-3 times weekly. Having at least twice weekly sessions provides the consistency of the training to promote the necessary physiological learning. In the PI's private practice, 20 sessions twice weekly was the most efficacious in achieving the physiological learning level desired. With the newest technology equipment used in this study, that enables a more specific and individualized focused treatment, it has been found that more frequent sessions are tolerated well and preferred by its recipients. Once started, people receiving NFB feel better in general and usually complete the entire 20 sessions.

The feedback provided will be multi-modal. The visual feedback feeds back various aspects of EEG-derived information, and this is complemented with an audio signal stream that similarly reflects the relevant aspects of the EEG. Finally, a tactile feedback capability is provided so that the feedback is experienced as immersive. Each of the signals corroborates and reinforces the others for a more compelling training experience.

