**Mid (4-6-week), End of Treatment (8-10-week) and 2-Month Follow-up Assessment Sessions (2.5 hours each session):** As above in the baseline assessment, participants will be given preparation instructions to ensure optimum test results. Participants will be instructed to have adequate rest the night before, and to have eaten a regular meal or snack prior to the assessment sessions. There will be an attempt to schedule all sessions at the same time of day for each individual participant, during a period of maximum alertness. One of the tests, the attention QIKtest will be administered early in the assessment session to minimize test fatigue. The participants will also complete several other questionnaires (see Table 5) during these 3 assessment sessions. In addition, the participants will indicate any changes on the demographic form, including changes in pregnancy status (or plans to become pregnant in the next five months) co-morbid health issues, participation in co-occurring classes or therapies and medications. Although the total time for completion of the questionnaires is estimated to be 120 minutes, a 2.5-hour time frame is given for rest periods, water break, slow test takers, and the answering of any questions the participants may have. Should a participant be unable to complete any assessment visit in person, the questionnaires may be mailed to the participant and mailed back at no cost to the participant. Decision to mail the questionnaires will be made by the study team on a case-by-case basis. The QIKtest cannot be mailed therefore this missing data point will be accounted for statistically at final analysis. Instructions will be mailed with the packet. See Appendix B for an example of the general information to be sent to the participants.

**Participation Termination by the Principal Investigator:** Possible reasons for study participation termination by the PI without concurrence by the participant include: concern for the individual's health and/or safety and participant non-compliance with study procedures (e.g., excessive number of missed NFB and/or assessment appointments; non-responsive to outreach attempts for rescheduling; non-responsive to control group phone calls.) Participants will be informed of this decision either in person, via telephone, or via letter. Participants who are terminated could enroll at a later date if they desire. However, the research team will review these requests on a case-by-case basis.

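### The per-protocol analysis targets the effect in adherers, but the only contrast written for it is high versus low attenders, not adherent neurofeedback participants versus randomised controls

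*Combined protocol and SAP*

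**What the plan says.** In the Statistical and Data Analysis Plan, after the list of outcomes, the secondary analysis is given this aim: "a per-protocol analysis will investigate the effect of the intervention in participants that adequately adhere to the intervention". The sentence goes on, after an e.g., to "participants that attend over half of the treatment sessions versus participants attend less half of the treatment sessions". Nothing more is specified for this analysis.

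The main analyses in the same section follow intention-to-treat: "participants are analyzed according to their group assignment regardless of the treatment received". The t-tests and the group-by-time model sit there and are not linked to the per-protocol set.

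Research Design and Methods gives the 20 one-hour sessions to the intervention group. For the other arm: "Participants in the control group will continue with their usual treatment and will receive a 15-minute call for eight weeks". After the final control assessment these participants are offered NFB and "will become part of the post-control intervention group".

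On expected attendance, Research Design and Methods says: "Once started, people receiving NFB feel better in general and usually complete the entire 20 sessions". Preliminary Studies reports that, in private practice, "less than 5% (n=19) did not complete their course of treatment of 10-40 sessions". Participation Termination by the Principal Investigator lists, among reasons for ending participation, "excessive number of missed NFB and/or assessment appointments".

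**The concern.** The aim and the stated contrast do not match. An effect of NFB in adherers needs a comparator that did not receive NFB. The written contrast instead divides people by how many sessions they attended, which is a behaviour after randomisation. Attendance may follow symptoms, motivation or early response. If people who attend would do better anyway, the contrast shows a difference even when NFB does nothing, and that difference would be reported as the effect in adherers. If few people attend under half, the contrast has little power. In either case it does not answer the question set for it.

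The same sentence leaves two smaller gaps. Someone who attends exactly 10 of 20 sessions belongs to neither group. Controls who later take NFB also attend sessions, and the sentence does not say whether those count.

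**Working it through.** The plan gives no sample size, power or expected adherence for this analysis, so there is no figure to reproduce. Its recruitment figure is consistent: 72/(1 - 0.28) = 100, or about 50 per arm.

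**1. Who falls on each side (randomised phase)**

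| Group | Sessions available | Over half | Under half |
|---|---|---|---|
| NFB arm | 20 | 11-20 | 0-9 |
| Control arm | none | nobody | nobody, or everybody if zero counts |

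Adherent NFB versus control appears on neither reading.

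**2. Bias, for illustration.** Assumptions, not document figures: no treatment effect; attendance propensity and outcome jointly normal with correlation r = 0.1-0.4; share q attending under half = 10% or 28%. The 10% is the low end of the dropout range cited under Power, and 28% is the plan's own dropout rate. With z = Phi^-1(q):

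- Within the NFB arm: r x phi(z) / [q(1 - q)]
- Adherers versus controls: r x phi(z) / (1 - q), which is q times the line above
- Adherers versus controls pooled with low attenders (equal arms): r x phi(z) x [1/(1 - q) + 1/(1 + q)]

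phi(z) is 0.1755 at q = 0.10 and 0.3366 at q = 0.28.

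| q | Within arm, r = 0.1 / 0.2 / 0.4 | Versus controls | Versus pooled group |
|---|---|---|---|
| 0.10 | 0.195 / 0.390 / 0.780 SD | 0.019 / 0.039 / 0.078 | 0.035 / 0.071 / 0.142 |
| 0.28 | 0.167 / 0.334 / 0.668 SD | 0.047 / 0.094 / 0.187 | 0.073 / 0.146 / 0.292 |

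**3. False positives.** Simulated t-test at nominal 5%, no effect, 50 in the NFB arm, half or three quarters of low attenders unmeasured at random, 20,000 runs per cell. A trial with fewer than two measured low attenders counts as not significant.

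| q | Unmeasured | Trials where the test can be run | r = 0.1 | r = 0.2 | r = 0.4 |
|---|---|---|---|---|---|
| 0.10 | half | 72% | 4.6% | 6.9% | 19.0% |
| 0.10 | three quarters | 36% | 2.2% | 3.1% | 7.5% |
| 0.28 | half | over 99% | 6.5% | 12.1% | 36.8% |
| 0.28 | three quarters | 87% | 5.3% | 7.6% | 20.8% |

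Adherers versus 50 controls, over the same cells: about 5-14%. Within-arm rates below 5% arise because the test often cannot be run.

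**4. Precision.** Detectable difference at 80% power, two-sided 5%: 2.80 x sqrt[v(1/n1 + 1/n2)]. For one visit v = 1. For the mean of four measures with the plan's correlation of 0.6 (compound symmetry), v = (1 + 3 x 0.6)/4 = 0.70.

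| Contrast | One visit | Mean of four |
|---|---|---|
| 36 v 14 (28% of 50 low) | 0.88 SD | 0.74 SD |
| 45 v 5 (10% of 50 low) | 1.32 SD | 1.10 SD |
| 36 adherers v 50 controls | 0.61 SD | 0.51 SD |
| 45 adherers v 50 controls | 0.58 SD | 0.48 SD |

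AR(1), which the plan names as an example, has v = 0.592 and gives 0.68 and 1.02 SD for the first two rows. All rows count every low attender as measured, which favours the within-arm contrast. For scale, the trial is designed around 0.49 SD between arms.

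**The case against.** The strongest reply is that the contrast is only an example. Elsewhere the plan uses the effect of the intervention to mean NFB versus control: the hypotheses are framed relative to the control group, and the main model has group as its between-subject factor. The authors may have meant to illustrate an attendance cut-off and to keep the same group comparison. That is a fair reading, and it means the documents do not establish that controls will be left out. But the example names both sides of a comparison, it is the only specification, and no control comparison is written for this analysis.

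A second reply is that controls attend zero sessions and so fall under less than half. Then they are pooled with poor attenders rather than omitted, and the within-arm figures do not apply. The pooled contrast still mixes untreated and partly treated people.

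A third is that the numbers rest on assumptions. This stands. Dropout is not the same as attending under half the sessions, since someone can leave after session 15 or miss sessions and still be assessed. At a correlation of 0.1 the false-positive rate is close to nominal.

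Three stronger inferences should be resisted:

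- A reader might take about 21% as the error rate for the cell with correlation 0.4, 10% low attenders and three quarters unmeasured. That is the rate only among the 36% or so of trials where the test can be run. Over all trials it is about 7.5%.
- A reader might apply the private-practice figure (19/432 = 4.4%) to 50 participants and expect about two low attenders. That figure is non-completion of courses of 10-40 sessions in other clients, not attendance under half in this trial.
- A reader might think the main result is compromised. It is analysed by assignment and does not use this contrast.

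**Conclusion.** The concern holds as a mismatch between aim and contrast in one secondary analysis. Followed as written, the plan does not yield the effect of NFB in adherers, on either literal reading. This much rests on the text alone.

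The size is unknown. Under the assumptions shown, the spurious difference is 0.17-0.78 SD within the NFB arm and 0.02-0.19 SD against controls. Unconditional within-arm false-positive rates are about 2-6.5%, 3-12% and 7.5-37% for correlations 0.1, 0.2 and 0.4. The imprecision does not depend on that correlation, but it does depend on the assumed share of low attenders. Severity is minor to moderate, and the intention-to-treat comparison is not touched.

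**What to change.** Replace the example in the Statistical and Data Analysis Plan with a specification that:

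- compares NFB participants who attend at least a stated share of sessions in the randomised phase with the randomised control arm;
- puts exactly 10 of 20 sessions on one named side;
- adjusts for the baseline value of the outcome;
- states that sessions and outcomes of the post-control intervention group are not used;
- labels the result non-randomised and supportive;
- reports how many NFB participants fall below the cut-off and how many of them have outcomes.

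If the high versus low attender comparison is kept, call it descriptive within the NFB arm. A complier-average estimate could be added but is optional.

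The cost is wording for one analysis, with no new data. Some selection bias remains. Without adjustment it is 0.02-0.19 SD under the assumptions above. Baseline adjustment multiplies it by between 1 (attendance unrelated to baseline) and 1 - 0.6 = 0.4 (attendance as correlated with baseline as with outcome), giving 0.01-0.19 SD. The Data Protection section says participant procedures are complete, so if outcome data have already been examined, date the change and label it post hoc.
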